1.0 Study Summary

Study Title	Prism Adaptation in Left Brain Stroke Rehabilitation
Study Design	Multiple baseline, delayed treatment approach
Primary Objective	To demonstrate the feasibility of adapted methods for assessing and treating spatial and motor function and pain in patients with aphasia and memory impairment.
Secondary Objective(s)	To demonstrate the feasibility of using information about lesion location from the radiology report to classify frontal vs. nonfrontal lesions
Research Intervention(s)/Interactions	Prism Adaptation Treatment (PAT) for spatial neglect in patients with aphasia and memory impairment
Study Population	Left brain stroke patients with aphasia and memory impairment
Sample Size	30
Study Duration for individual participants	7 weeks
Study Specific Abbreviations/ Definitions	DVPRS: Defense and Veterans Pain Rating Scale KF-NAP: Kessler Foundation- Neglect Assessment Protocol PAT: Prism Adaptation Treatment WMFT: Wolf Motor Function Test
Funding Source (if any)	Department of Veterans Affairs

2.0 Objectives

2.1 Specific Aim 1: To demonstrate the feasibility of adapted PAT procedures in patients with aphasia and memory impairment. Hypothesis: Adapted methods for PAT administration in patients with aphasia are feasible. Even in the presence of memory disorder detecting a treatment signal is possible.

Specific Aim 2: To demonstrate the feasibility of adapted methods for assessing spatial and motor function and pain in patients with aphasia and memory impairment. Hypothesis: Adapted methods for assessing spatial and motor function and pain in patients with aphasia and memory impairment are feasible.

Specific Aim 3: To demonstrate the feasibility of using information about lesion location from the radiology report to classify frontal vs. nonfrontal lesions. Hypothesis: Lesion classification results from radiology reports and brain mapping methods are consistent, confirming this adaptation provides a clinically

accessible, reliable way to identify brain-based predictors of optimal PAT response in future studies.

2.2 Specific Aim 1: Adapted methods for PAT administration in patients with aphasia are feasible. Even in the presence of memory disorder detecting a treatment signal is possible.

Specific Aim 2: Adapted methods for assessing spatial and motor function and pain in patients with aphasia and memory impairment are feasible.

Specific Aim 3: Lesion classification results from radiology reports and brain mapping methods are consistent, confirming this adaptation provides a clinically accessible, reliable way to identify brain-based predictors of optimal PAT response in future studies.

3.0 Background

3.1 Every year about 15,000 Veterans are hospitalized for stroke (Cowper, 2004). Given the expected rapid and significant increase in Veterans above age 65 over the next decade (NCVAS, 2011) and the reality that the risk of stroke more than doubles each decade after age 55 (CDC, 2010), our aging Veterans are at an ever-increasing risk of joining the 80,000 Veterans who are already suffering from stroke-related long-term disability (Jia et al., 2006). Stroke and its complications represent the most frequent cause of adult-onset disability in the US, and post-acute stroke care is among the fastest-growing federal expense categories (CDC, 2003; Buntin et al., 2010). Currently, there are separate and modality-specific treatment pathways for cognitive and motor impairments, and pain, in stroke survivors. Clinicians can access guidelines for evidence-based practice from the American Heart Association (Winstein et al. 2016), Veterans Administration/Department of Defense (Management of Stroke Rehabilitation Working Group 2010) and individual professional organizations such as the American Occupational Therapy Association (Wolf and Nilsen 2015). However, current guidelines and care pathways still match single conditions to single methods of rehabilitation.

Because of the limited rehabilitation resources available to address Veteran functional disability after stroke, we need to identify feasible treatments acting on more than one recovery target. Multi-target therapies could also improve rates of diagnosis for hidden disabilities, such as spatial neglect and pain, which are under-identified, and under-treated (Edwards et al. 2006; Chen et al. 2013; Widar and Ahlstrom 2002). Because the care system does not yet emphasize multi-target treatments, stroke survivors can experience a fragmented interprofessional care process, in which treatment of some disabling conditions, but not others, leads to incomplete recovery and reductions in quality of life (Haynes et al. 2015). Lack of care efficiency can also increase care costs, prolong hospital stays, and increase utilization of other healthcare services

(Olson et al. 2013). Combining interventions for cognitive and motor impairments, and pain, and systematically tracking treatment effects would help streamline the process for >50% of Veteran stroke survivors who have both visible and hidden disabilities (Mahon et al. 2017; Yelnik et al. 2011; Management of Stroke Rehabilitation Working Group 2010), and help ensure that they receive optimal services during the post-acute period. By establishing the feasibility of applying standardized methods for assessment, treatment and prediction of treatment response in patients with left brain stroke, we contribute to two broad goals of this line of research.

GOAL 1: To develop clinically translatable, multi-target treatments for broad application in stroke.

Prism adaptation treatment (PAT; Barrett, Goedert, and Basso 2012) is a 10-day spatial retraining treatment regimen developed to treat the disabling post-stroke visual-cognitive disorder, spatial neglect (Barrett and Houston 2019; Heilman, Watson, and Valenstein 2012; Corbetta and Shulman 2011; Hillis, Mordkoff, and Caramazza 1999). Although many studies demonstrated the benefit of using PAT to treat spatial neglect (see Yang et al., 2013 for review), studies have also demonstrated positive effects on motor function (see Champod et al., 2016) and on pain. Direct measurement of functional movements in the laboratory supported a beneficial effect of PAT on arm movements, center of gravity, and posture (Fortis et al. 2011; Shiraishi et al. 2008; Nijboer et al. 2014). In addition, case series data indicate that PAT can be used as a non-pharmacologic treatment to reduce post-stroke pain (Sumitani et al. 2007; Christophe et al. 2016), which occurs in about half of stroke survivors, (Naess, Lunde, and Brogger 2012; Lundstrom et al. 2009; Hansen et al. 2012) adversely affecting cognitive and functional independence, and quality of life (Harrison and Field 2015). As we note above, PAT was developed for spatial retraining. Because spatial function and other cognitive processes are potentially distributed and highly interactive with other functional domains, spatial retraining may provide a “back door” to improve motor recovery and somatic experience through pain relief. Given the high rates at which stroke patients experience spatial-motor-sensory impairments, and in the absence of integrated treatment plans that encompass the three domains depicted in Figure 1, a multi-target treatment such as PAT is highly desirable. Although available controlled trials of PAT and other spatial neglect treatments indicated that these therapies can restore adaptive movements and functional abilities, studies have been conducted exclusively in people with right brain stroke (Yang et al. 2013). Clinicians are unlikely to administer PAT routinely for stroke survivors when there is no evidence that doing so will yield therapeutic benefit in left brain stroke. Additionally, clinicians may hesitate to apply PAT in patients with aphasia and memory impairments, which are common after left brain stroke (Pedersen et al., 1995; Eskes & Barrett 2009). Thus, we identified the potential for a high-risk, high-reward study that demonstrates feasibility of standardized assessment and treatment methods in

left brain stroke patients, to open a path for broad application of PAT in both left and right brain stroke survivors.

GOAL 2: To develop clinically translatable assessment methods for diagnosis and identification of subgroups who will benefit from multi-target treatments.

Patient-centered, precision medicine is tailored to brain-based factors relevant to recovery in an individual stroke survivor. Genetic risk factors are often considered in predictors of stroke recovery (Cramer, 2008). Cognitive deficits also predict response to rehabilitation (Dignam et al., 2017), possibly because they interact with motor brain systems (Barrett, Boukrina, and Saleh 2019) or alter the applicability of global outcome measures (Bosetti et al., 2017; Cramer, 2007). The potential impact of cognitive deficits on rehabilitation outcomes highlights the need for comprehensive and accurate diagnosis to guide clinical decision-making.

In addition, brain physiology and anatomy may also define patient subgroups with better response to specific rehabilitation methods (e.g. non-invasive brain stimulation; Plow et al., 2016; Nouri & Cramer, 2011). Although patients across a range of brain lesion locations may experience treatment benefit from PAT (see Yang et al., 2013 for a review), we and others reported that the presence of frontal lobe cortical lesions predicts optimal response to treatment, and subsequent recovery of functional performance in stroke-induced spatial neglect (Chen et al., 2014; Goedert et al., 2018; Gutierrez-Herrera et al., 2018). These experiments were carried out exclusively in right brain stroke-- no data about brain-behavior relationships in recovery from neglect after left brain stroke, with or without treatment, is available. To develop PAT in future large-scale studies as a multi-target treatment for use in patients with both left brain stroke and right brain stroke, first requires determining whether stratifying patients by frontal lobe lesions reveals differences in treatment benefit. The presence of large differences in PAT response related to lesion location would affect the design and evaluation of PAT for stroke rehabilitation as well as eventual clinical decision-making for assigning PAT to eligible stroke survivors. However, clinicians in rehabilitation settings typically obtain information about lesion location from a patient's medical record. Before guidelines for PAT patient selection can be broadly implemented, we must establish that obtaining information about lesion location from the radiology report, as compared to research-based brain mapping methods, is a feasible and reliable method of categorizing lesions.

3.2 Preliminary Study 1: Members of our team have demonstrated that administration of PAT using standardized methods is feasible and yields therapeutic benefits in right brain stroke (Barrett et al. 2012). Purpose: Expert clinicians who assess and treat invisible disabilities like spatial neglect use a variety of rehabilitation techniques (Chen et al. 2017) depending on barriers present, recovery stage, and characteristics of the deficit. However, clinicians carrying out routine care find a large number of choices for spatial neglect

treatment confusing and impractical. Methods: Of all of the treatments available, prism adaptation treatment (PAT) was identified as being the most feasible (Barrett, Goedert, & Basso 2012). PAT improved spatial neglect in multiple randomized studies (Yang et al. 2013), and is also time-efficient, requiring only 10, short, daily sessions (20-30 minutes), with no components of treatment that need to be cross-implemented, carried out during other times of day, or co-administered as part of other therapies (Barrett & Houston 2019). PAT was manualized, and in a network of inpatient rehabilitation sites that received training, the time for therapists to learn how to administer PAT is less than a day. Results: PAT improves daily life function (Champod et al. 2016), and improvements are noted in self-care, reading and writing, and even wheelchair navigation and posture. Conclusions: Standardizing the administration of PAT allowed for packaging the care process for training of more than 100 therapists in a nationwide practice-based network to deliver right brain rehabilitation (Barrett, 2019). This study will extend this work by establishing the feasibility of adapted PAT procedures in left brain stroke patients with aphasia and memory impairment (Aim 1).

Preliminary Study 2: Members of our team have standardized methods for assessment of spatial neglect in right brain stroke (Chen et al. 2012; Chen et al. 2015). Purpose: In 60-80% of people with spatial neglect, care professionals do not diagnose or document the disorder during routine inpatient rehabilitation (Chen et al. 2013; Edwards et al. 2006). Because it has an independent, adverse effect on multiple domains of daily life function, assessing spatial neglect via functional performance is the first step to assigning treatment and speeding neurological recovery. Methods: The semi-quantitative, examiner-rated Catherine Bergego Scale (CBS), which is a reliable, validated 10-item questionnaire to detect and evaluate spatial neglect severity (Azouvi 2016; Chen et al. 2015; Azouvi et al. 2003) was adapted. The Kessler Foundation Neglect Assessment Process (KF-NAP®), a manualized process was added which provides detailed instructions and specifies that administration takes place by one examiner during a single assessment session (Chen et al. 2012; Chen, Chen, et al. 2015). Results: Catherine Bergego Scale via the KF-NAP® is an excellent predictor of rehabilitation outcomes (Chen et al. 2015) and its simplicity is appealing to clinicians, who report its adoption in 13 countries, and more than 40 US inpatient and outpatient care settings. Conclusions: The KF-NAP® is a systematic, evidence-based valid method of spatial neglect assessment after right brain stroke. This study will extend this work by establishing the feasibility of adapted KF-NAP® procedures for assessing spatial neglect in left brain stroke patients with aphasia and memory impairment (Aim 2).

Preliminary Study 3: Members of our team have developed standardized methods for assessment of motor function in stroke patients without cognitive impairment (Wolf et al., 2001). Purpose: Greater than 70% of stroke patients suffer motor impairments (Mohr et al., 1993), making assessment and treatment

of motor function a high priority in stroke rehabilitation. The Wolf Motor Function Test (WMFT) is a time-based assessment that quantifies functional ability of upper extremities through a series of tasks ranging in complexity and proximal to distal involvement. WMFT requires few tools and minimal training for administration, making it ideal for clinical use. Methods: Healthy older adults and patients with chronic stroke were administered the WMFT and the upper extremity portion of the Fugl-Meyer Motor Assessment (FMA) at two time points 12-16 days apart. Results: The WMFT and FMA demonstrated agreement between raters at both time points. WMFT scores for upper extremities of healthy older adults were significantly different from those of the stroke patients. The WMFT and FMA scores for the more affected extremity in stroke patients were related. Conclusions: The WMFT is a valid and reliable assessment of motor function in stroke patients without cognitive impairment. This study will extend this work by establishing the feasibility of adapted WMFT procedures for assessing motor function in left brain stroke patients with aphasia and memory impairment (Aim 2).

Preliminary Study 4: Using brain mapping methods, members of our team have shown that right brain stroke patients with frontal lesions respond optimally to PAT (Chen et al., 2014; Goedert et al., 2018). Purpose: Research with neurologically unimpaired individuals suggests that prism adaptation may stimulate lateralized motor-related spatial systems (Fortis, Goedert, and Barrett 2011) linked to frontal cortical brain networks (Ghacibeh et al. 2007). Thus, the presence or absence of frontal brain lesions may affect PAT response. Methods: We had trained raters categorize patients based on their clinical brain images: as having, or not having, a frontal cortical brain lesion (Chen et al. 2014; Goedert et al. 2018). Results: In both studies, patients with frontal brain lesions experienced a more robust therapeutic response to PAT, based on functional performance testing. Although in the first study, medial temporal structures also appeared to play a role in PAT response, this was not confirmed in the second study. Conclusions: A frontal cortical lesion predicts optimal PAT response after right stroke. However, clinical decision-making based on brain mapping with trained raters is not feasible in the clinical environment. This study will extend this work by determining whether obtaining information about lesion location from the medical record is a feasible, reliable way to identify patients with frontal vs. nonfrontal lesions (Aim 3).

3.3 This study is the first to systematically investigate the feasibility of using adapted PAT treatment procedures and spatial-motor-sensory assessments in left-brain stroke patients with aphasia and memory impairment, as well as clinically-accessible methods for identifying patients with optimal response to PAT. This line of research lays the foundation for a potential paradigm shift in the focus of rehabilitation research to PAT as a multi-target treatment to improve spatial function, adaptive movements, functional independence, and pain-free somatic experience. In addition, this study could change the conventional

structure of stroke rehabilitation trials, most of which have not measured the impact of cognitive treatments on motor function, or vice versa, and do not assess the concurrent effect of either cognitive or motor treatment on pain.

4.0 Study Endpoints *

4.1 We will assess four key aspects of feasibility of our adapted assessment and treatment procedures: acceptability, implementation, adaptation, and limited efficacy testing (Bowen et al., 2009). See Table 1. Acceptability: We will use the Client Satisfaction Questionnaire (CSQ-8; Attkinson & Zwick, 1982; Larsen et al., 1979) to assess satisfaction and perceived value of PAT. We will use the Credibility/Expectancy Questionnaire (CEQ; Devilly & Borkovec, 2000) to assess the degree to which PAT is believable, convincing and logical (credibility) and the expectations for PAT-induced improvement (expectancy). The CSQ-8 and CEQ have been used in patients with subjective cognitive impairment (Foster et al., 2018). Implementation: We will record attendance and completion rates to determine whether KF-NAP®, WMFT and PAT can be carried out as planned. Adaptation: Each session, study staff will complete checklists from the KF-NAP®, the WMFT, and the KF-PAT™ manual (Chen, 2015) to track assessment and treatment fidelity. Notations will be made when modifications to administration methods are required. For the brain mapping, trained raters will map brain lesions using the method from Preliminary Study 4. Then, a blinded neurologist will classify participants as having “frontal” or “nonfrontal” lesions. Using radiology reports, lesions will be classified as “frontal” based on use of that word or “anterior” “premotor” “prefrontal” or “precentral” or as “nonfrontal” if none of those words are present. Limited Efficacy Testing: To detect the acquisition and maintenance of a treatment signal, we will assess spatial-motor-sensory and functional recovery over 7 weeks (Figure 2). We will assess: 1) Functional disability, measured by activities of daily living using the Barthel Index (Mahoney & Barthel 1965) and cognitive and motor function with the FIM or FONE-FIM; 2) Spatial neglect, measured by the Behavioural Inattention Test-conventional subtest (Wilson et al., 1987) and CBS via the KF-NAP® (Chen et al. 2012); 3) Motor function, measured by the WMFT (Lin et al., 2009); and 4) Pain, measured by the Defense and Veterans Pain Rating Scale (Polomano et al. 2016), which includes numbers along with pictures and colors to facilitate nonverbal rating of pain. Assessments will be administered by a trained examiner.

TABLE 1. Study Endpoints.

Key Area	Aim	Question	Analysis on Outcome of Interest
Acceptability	1	
• Do left brain stroke patients view PAT as a satisfactory and credible tool for rehabilitation?	
• Range of post-PAT satisfaction ratings on CSQ-8• Range of credibility and expectancy ratings on CEQ (pre and post PAT)
Implementation	1,2	
• Can KF-NAP®, WMFT, DVPRS and PAT be implemented as planned in left brain stroke patients?	
• Completion rate for KF-NAP®, WMFT, DVPRS and full 10-session PAT
Adaptation	1,2,3	
• What modifications are necessary for implementation of KF-NAP®, WMFT and PAT in left brain stroke patients?• Is classification of lesion location from the medical record consistent with classification using brain mapping?	
• Number and type of modifications to KF-NAP®, WMFT and PAT protocol• Percent agreement on presence or absence of frontal lesion between radiology report and brain mapping
Limited Efficacy Testing	1,2	
• Is there promise for application of PAT in left brain stroke patients?	
• Visual inspection of recovery trajectories on spatial-motor-sensory and functional assessments over 7 weeks to detect the acquisition and maintenance of a treatment signal

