Widar, M., and G. Ahlstrom (2002). Disability after a stroke and the influence of long-term pain on everyday life. Scand J Caring Sci, 16, 302-10.

Wilson, B., J. Cockburn, and P. Halligan (1987). Development of a behavioral test of visuospatial neglect. Archives of Physical Medicine and Rehabilitation, 68, 98-102.

Winstein, C. J., J. Stein, R. Arena, B. Bates, L. R. Cherney, S. C. Cramer, F. Deruyter, J. J. Eng, B. Fisher, R. L. Harvey, C. E. Lang, M. MacKay-Lyons, K. J. Ottenbacher, S. Pugh, M. J. Reeves, L. G. Richards, W. Stiers, R. D. Zorowitz, Council on Cardiovascular American Heart Association Stroke Council, Council on Clinical Cardiology Stroke Nursing, Care Council on Quality of, and Research Outcomes (2016). Guidelines for Adult Stroke Rehabilitation and Recovery: A Guideline for Healthcare Professionals From the American Heart Association/American Stroke Association. Stroke, 47, e98-e169.

Wolf, S. L., Catlin, P. A., et al. (2001). Assessing Wolf motor function test as outcome measure for research in patients after stroke. Stroke, 32, 1635-1639.

Wolf, T.J., & D. M. Nilsen (2015). Occupational therapy practice guidelines for adults with stroke. Bethesda, MD: American Occupational Therapy Association.

Yang, N. Y., D. Zhou, R. C. Chung, C. W. Li-Tsang, and K. N. Fong (2013). Rehabilitation Interventions for Unilateral Neglect after Stroke: A Systematic Review from 1997 through 2012. Frontiers in Human Neuroscience, 7, 187.

Yelnik, A. P., A. Schnitzler, P. Pradat-Diehl, J. Sengler, J. P. Devailly, P. Dehail, C. D'Anjou M, and G. Rode. (2011). Physical and rehabilitation medicine (PRM) care pathways: "stroke patients". Ann Phys Rehabil Med, 54, 506-18.

Statistical Analysis Plan

Data on four key areas of feasibility will be analyzed using descriptive statistics, including measures of frequency, central tendency, dispersion and variation. **See Table 1.**

Key Area	Question	Analysis on Outcome of Interest
Acceptability	
 Do left brain stroke patients view PAT as a satisfactory and credible tool for rehabilitation? 	
 Range of post-PAT satisfaction ratings on CSQ-8 Range of credibility and expectancy ratings on CEQ
Implementation	
 Can KF-NAP®, WMFT, DVPRS and PAT be implemented as planned in left brain stroke patients? 	
 Completion rate for KF-NAP®, WMFT, DVPRS and full 10-session PAT

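### KF-NAP and WMFT sessions given in modified form enter the efficacy trajectories unmarked, so a change in administration around PAT onset can imitate or hide a treatment signal in an individual's plot

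*Combined protocol and SAP*

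**What the plan says.** Under Adaptation, section 4.1 and the SAP both provide for a record at every session: "Each session, study staff will complete checklists from the KF-NAP®, the WMFT, and the KF-PAT™ manual". They add: "Notations will be made when modifications to administration methods are required". Table 1 asks which modifications prove necessary, so departures from standard administration are expected. Their planned analysis is "Number and type of modifications to KF-NAP®, WMFT and PAT protocol".

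Under Limited Efficacy Testing, the same section takes spatial neglect from the conventional subtest of the Behavioural Inattention Test (BIT) and the CBS scored through the KF-NAP, and motor function from the WMFT. Section 6.2 has spatial and motor function assessed weekly. The protocol's Table 1 gives the analysis as "Visual inspection of recovery trajectories on spatial-motor-sensory and functional assessments over 7 weeks to detect the acquisition and maintenance of a treatment signal". The SAP's table repeats the purpose without the visual inspection, and the SAP opens with "Data on four key areas of feasibility will be analyzed using descriptive statistics, including measures of frequency, central tendency, dispersion and variation".

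Section 6.1 starts PAT after two baseline sessions in Group 1 and after four in Group 2.

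**The concern.** Two instruments serve two purposes that pull against each other. Adaptation invites staff to change how the test is given; Limited Efficacy needs successive scores from one participant to be comparable. Nothing in the protocol or SAP links the two: there is no default of constant administration within a participant, no mark on the plot for a modified session, and no separate reading of those sessions.

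Both scores could plausibly respond to how the test is given. Section 3.2 says "The Wolf Motor Function Test (WMFT) is a time-based assessment", and describes the CBS as rated by the examiner. It supports the WMFT in stroke patients without cognitive impairment and the KF-NAP after right brain stroke, so it offers no evidence that modified and standard scores are interchangeable in this population.

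At stake is the answer to Table 1's question whether PAT shows promise, and the part of the Aim 1 hypothesis that says a treatment signal can be detected. With visual reading and no decision rule, a step produced by a changed administration looks the same as acquisition of an effect. A shift in the other direction could conceal one.

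**Working it through.** The plan states no figure to reproduce. The check sets the provisions side by side and then sizes the artefact in units of an unknown shift.

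**Provisions compared**

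| Question | Where | Answer |
|---|---|---|
| Are modifications recorded by session? | 4.1; SAP, Adaptation | Yes, on checklists |
| How are they analysed? | Table 1 in both documents | Number and type only |
| Do the same scores feed efficacy? | 4.1; SAP, Limited Efficacy | Yes: CBS via KF-NAP, and WMFT |
| Is administration held constant, or are modified sessions marked or read apart? | 4.1, 6.2, 17.1, 17.3, SAP | No such rule |
| Are assessors blinded to phase? | 4.1 | Not stated; only the neurologist classifying lesions is called blinded |

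That a modification may begin at any session is an inference from the per-session checklists and the absence of a restriction. The protocol does not say it outright.

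**Size for one participant.** Assumptions: no PAT effect; one lasting modification shifts the score by d (either sign); S weekly assessments, the first b of them baseline; session k is the last unmodified one. Section 6.2 can be read as S = 7 or 8; section 6.1 gives b = 2 or 4. The apparent change, post-baseline mean minus baseline mean, is:

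- d × k/b if k < b (modification starts within baseline);
- d × (S − k)/(S − b) if k ≥ b (starts after baseline).

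At k = b, the first assessment after baseline, this is the full 1.0d. If k is equally likely to be any of 1 to S − 1:

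| S | b | Starts after baseline, (S − b)/(S − 1) | Mean apparent change |
|---|---|---|---|
| 7 | 2 | 5/6 = 83% | (0.5 + 3.0)/6 = 0.58d |
| 7 | 4 | 3/6 = 50% | (1.5 + 2.0)/6 = 0.58d |
| 8 | 2 | 6/7 = 86% | (0.5 + 3.5)/7 = 0.57d |
| 8 | 4 | 4/7 = 57% | (1.5 + 2.5)/7 = 0.57d |

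Averaged over the two groups, 67% (S = 7) or 71% (S = 8) of such modifications start after baseline.

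**What the stagger removes.** At sessions 3 and 4, Group 1 has started PAT and Group 2 is still in baseline. Under the same assumption the chance of being already modified at session j is (j − 1)/(S − 1) in both groups. For S = 7 that is 2/6 at session 3 and 3/6 at session 4 in each group, so the expected between-group difference is zero. If modifications instead begin with PAT (session 3 in Group 1, session 5 in Group 2) in a share p of participants, the difference at sessions 3 and 4 is p × d. The stagger therefore removes drift tied to session number and leaves change tied to PAT onset. It does nothing for a single plot.

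**The case against.** The strongest reply is the design. Staggered starts with computer-generated assignment exist to separate time trends from treatment, and the calculation confirms that modifications accruing by session number cancel between groups. That stands. It does not reach individual plots. Nor does it reach changes prompted by PAT contact: ten treatment sessions in two weeks (section 5.1) follow weekly assessments, and examiners are not said to be blinded or separate from treating staff.

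Second, a reader might infer that staff learn what each participant needs, that later sessions therefore carry more help, and that the trajectories are biased toward benefit. The documents do not support this. They do not define a modification or say that help increases; the need could be greatest at first exposure and then fade, which would work against PAT.

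Third, there are partial safeguards. The BIT is a second neglect measure outside the modification endpoint, so an artefact confined to the KF-NAP could show as disagreement between the two. No second measure is listed under motor function. Section 17.3 promises reliability checks without saying what they cover. The manuals and checklists are not in the documents and may define a standard adapted version.

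Fourth, this is a descriptive feasibility study with a session-level log, so modified sessions could be examined afterwards. That is true and limits the severity. A check devised once the plots have been seen is still weaker than one written beforehand.

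**Conclusion.** The point holds in a limited form. Under the plan as written, a change in KF-NAP or WMFT administration at or after PAT onset can be mistaken for, or can mask, a treatment signal in an individual's trajectory. For a lasting shift d, the apparent change is up to 1.0d, and 0.57d to 0.58d on average under a uniform start. At group level only modifications linked to PAT onset remain a threat.

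A reader might want a figure in standard deviations. Supposing that 25–50% of participants are affected by 0.3–0.5 SD gives 0.25 × 0.3 = 0.075 to 0.5 × 0.5 = 0.25 SD in the mean. Neither factor is in the documents, the sign is open, and the product ignores the stagger, so it should not be used as an estimate of bias. The conclusion is confined to these two instruments and to the Limited Efficacy reading; the Adaptation endpoint itself is unaffected.

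**What to change.** In section 4.1 and the SAP, under Limited Efficacy Testing:

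1. Mark on each CBS and WMFT trajectory plot every session with a logged modification to that instrument.
2. Prespecify a second reading of these two measures that compares only sessions before and after PAT that were given in the same way. Report how many participants have no such comparison.
3. As a default, carry the administration in use at the end of baseline into later sessions. New modifications stay allowed and are still counted under Adaptation. A freeze at the first session would be wrong here, because it would fix the method before staff know what is needed, which is what Adaptation sets out to learn.

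The cost is some wording and a flag taken from checklists already completed; no new visits or data are required. The downside is loss from the second reading. A participant whose lasting modification begins at the first assessment after PAT onset has no matching session and drops out for that measure; a later start leaves only the unmodified sessions before it. If, purely as an assumption, 25–50% of the target 30 were lost in this way, that would be 0.25 × 30 = 7.5 to 0.5 × 30 = 15, or about 8 to 15 participants. The first reading keeps everyone, and the number lost is itself a useful feasibility result.
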